**3. Abstract:**

In this Phase II SBIR project we will enhance a wireless WiFi-based insole that was designed and successfully tested and evaluated during a Phase I trial with elderly persons with dementia and their caregivers, and then investigate its efficacy in reducing caregiver activity and burden, and improving caregiver quality of life. An estimated 5.4 million Americans had Alzheimer's disease in 2016 and a 50% increase in this number is expected by 2030. The majority of these patients (70%) will live at home where they receive 75% of their care from informal, unpaid caregivers, such as family members, friends, and neighbors. These caregivers provide valuable services, often at great economic and psychological cost to themselves. In 2015, over 18 billion hours of unpaid care were estimated to have been provided by over 15 million caregivers. Around 15% of them quit their job or reduced their hours to provide this care. This translated to nearly \$222 billion dollars of unpaid care in a single year. In the absence of a cure, dementia patients and caregivers prioritize quality of life as their most valued outcome. Technological solutions to assist caregivers in locating wandering patients have been introduced. However, existing solutions lack reliable functionality for indoor environments, require significant infrastructure enhancement, or burden both patient and caregiver with the use of non-discreet electronics packages that must be worn as wristbands or belt mounts. There exists an unmet need to support caregivers by providing a comprehensive localization solution of the patient relative to the caregiver that works both indoors and outdoors with little to no additional infrastructure required.

ASTER Labs' device, called Activlink, is a patient localization solution optimized to assist monitoring by primary and secondary caregivers of dementia patients in indoor building environments. The goal is to increase quality of life for caregivers by providing a highly-accurate localization of a patient's position, combined with real-time alerts of a patient's wandering movements. Perpetual safety concerns and the demands of constantly monitoring their patient result in caregiver's often reported reduced abilities to function in normal daily activities. Activlink provides on-demand access to real-time location visualization within a home or public building, both while in relatively close proximity to the patient and remotely, for remotely-located family members or secondary caregivers wishing to monitor the patient's location. The innovative concept design for this system provides continuous localization capabilities, so that the quality of life for both patient and caregiver may be enhanced by allowing both to move throughout a home or in large indoor spaces like malls, airports, and medical centers. In this project, ASTER Labs will use WiFi and inertial sensor dead reckoning technologies to create a highly unique, accurate, and practical indoor localization solution. This Phase II SBIR will evaluate the efficacy of the WiFi-based insole to provide caregivers with augmented patient awareness, helping to improve their immediate quality of life by reducing their direct burden of continuous oversight of their person in care. Evaluation will be done using semi-structured interviews and participant observation data collected on persons with moderate to mild dementia, their family caregivers, and professional care providers via an embedded randomized controlled evaluation.

**4. Background:**

Recent research indicates longer life expectancy for America's seniors than at any prior time, with 65 year olds expected to live almost two additional decades. In the next 25 years, the United States' elderly population expects to see an 80 percent growth [1]. Coupling these projections with the advance of the *baby boomers*, the roughly 46 million current seniors will soon see large additions to the elderly population. For the oldest seniors, this population increase has meant a heightened prevalence of aging-

associated conditions and diseases. In 2016, 14% of all American seniors over 71 years old were diagnosed with dementia, or almost 5.5 million people [2]. In the *oldest old*, those seniors over age 90, that occurrence spiked to 37.4% [3]. Lacking methods to prevent, cure, or slow the progression of Alzheimer's disease (AD) and similar variations of the syndrome, one in every three seniors is expected to die with some form of dementia [4]. In the coming four decades, the number of functionally dependent Americans with AD, predicted to be around three times the current number, may overwhelm the eldercare system and significantly tax the availability of quality long-term healthcare. AD, the most common form of dementia, characteristically worsens significantly through its progression. The early stages involve symptoms of forgetfulness, with patients unable to recall familiar people's names or recent events [5]-[8]. In its middle stages, disorientation, memory loss, and confusion tend to see a marked increase, so that recalling appointments, recognizing family members, and remembering important tasks like taking medication becomes much more difficult [5]-[8]. It is often at these stages that patients will experience heightened anxiety associated with the cognitive loss that leads to personality changes, loss of sense of self, and frustrations with the newly imposed lack of independence [9]. Caregiver's quality of life therefore is distinctly impacted by a patient's behavioral changes like depression, fear, frustration, and grief [10].

In the absence of a cure, dementia patients and caregivers prioritize quality of life as their most valued outcome [11]. Safety concerns impact quality of life and are a primary reason for dementia patients' relocation from home [12]. Significant economic cost is associated with the treatment and care of AD patients, who can expect to pay near triple the cost for healthcare and long-term care [3],[13]. Recent estimates indicate informal, unpaid caregivers, such as family members, friends and neighbors, provide three-quarters of the care for patients suffering from dementia, 70% of whom are cared for at home full or part time [15],[16]. New studies show that informal in-home patient monitoring has the potential to reduce frequency of hospital and emergency room visits and delay institutionalization [17], [18]. Despite this benefit, the economic cost has become overwhelming. In 2015 alone, an estimated 18.1 billion hours of informal, unpaid care were provided by over 15 million caregivers, numbers which translated to almost \$221.3 billion in unpaid caregiving in the United States [19],[1]. Accompanying the financial burden, informal caregivers cite lost work hours, leaves of absence, and career abandonment as common work-related issues associated with the conflict between caregiving and career [20]. In more serious cases, psychological effects and shortened lifespan have been attributed to the demands of caregiving [15],[16],[20]. Monitoring dementia patients typically requires diligent and continuous attention, making feelings of isolation common [21]-[23]. Inabilities to interact in normal social settings and activities and difficulty caring for non-mobile dementia patients add to the list of stress factors associated with caregiving [24],[25].

While progression of each patient's dementia varies, one of the most common and burdensome similarities in behavior is wandering, or *dementia elopement* [14],[25]. It is estimated that 60% of AD patients exhibit this behavior and are at risk of disorientation and associated injuries [26],[27]. Studies show that half of all wanderers lost for 24 hours or more will be injured or die [28],[29]. The advancement of AD tends to increase the disorientation in time and space, increasing the probability of elopement behavior [2],[30],[31]. A system providing caregivers the ability to localize a wandering patient would reduce the emotional burdens of caregiving and enhance the safety of dementia patients. This localization tool, which automates the monitoring process and provides rapid alerts when a patient's movement indicates undesired wandering, holds significant potential. The tool would renew caregiver's abilities to function in normal daily activities and increase economic freedom from the great cost associated with caring for a patient or loved one suffering from dementia.

## **5. Specific aims:**

The efficacy of the *Activlink* system offering localization information to improve caregiver will be evaluated in two studies. Study 2a will use the insole system with dementia patients residing in skilled or memory care. Data regarding caregiving activity will be collected from their paid professional care providers. Study 2b will use participant localization data collected on 80 independently dwelling mild dementia patients. In this case data will be collected from their unpaid family caregivers. Both studies will result in evaluating the efficacy of the WiFi-based insole to provide caregivers with augmented patient awareness, helping to improve their immediate quality of life by reducing their direct burden of continuous oversight of their person in care.

## **6. Research plan:**

The proposed study is the second phase of a larger, multi-phase study: Accurate WiFi-Based Localization of Dementia Patients For Caregiver Support. The first phase involved assessing the feasibility and utility of the *Activlink* insole. The specific aims of the first phase were to define the architecture and build a prototype *Activlink* insole, develop the software solution of the WiFi-based localization, and evaluate the feasibility of using the insole and associated application for providing caregivers a method to monitor the location of their demented patient (see page 15 of 57 of the NIH Grant Proposal). Phase I goal was fully accomplished and feasibility was successfully shown via both technical evaluation of the insole prototype system as well as positive responses in the Phase I focus study evaluation (see page 19-24 of the NIH Grant Proposal). As all the Phase I aims were achieved, Phase II builds upon the discoveries and enhancements raised during Phase I, and results in the development of a market-ready insole device tested and evaluated in a large human study. There are two aims in Phase II. The first aim targets the creation of a market-ready insole sensory system with cross-platform mobile application. The second aim of Phase II relates specifically to the purpose of the proposed study. This study which encompasses aim two of Phase II, focuses on evaluating the efficacy of the *Activlink* system by offering localization and wandering status of individuals with dementia to improve caregiver quality of life. Specifically, this study (Phase II, aim 2) will be completed using two separate studies, Studies 2a and 2b. Study 2a will use the insole system with dementia patients residing in skilled or memory care. Data regarding caregiving activity will be collected from their paid professional care providers. Study 2b will use participant localization data collected on 80 independently dwelling mild dementia patients. Both studies will result in evaluating the efficacy of the WiFi-based insole to provide caregivers with augmented patient awareness, helping to improve their immediate quality of life by reducing their direct burden of continuous oversight of their person in care.

### Design

Both studies will involve a counterbalanced within-subject design. Specifically, each target patient will randomly be assigned to either have the technology or not have the technology applied for a period of three months, followed by three months of the opposite condition. Caregivers will provide caregiver ratings twice monthly during these two epochs. For Study 2a we will deploy 5 units during the initial 3 months and have 5 patients unmonitored. Then these patients will switch conditions. For Study 2b, we will deploy 20 units at a time and have a total of 4 cohorts (monitored then unmonitored months 13-18, unmonitored then monitored months 13-18, monitored then unmonitored months 19-24, unmonitored then monitored months 19-24). For Study 2b, caregivers will be mailed questionnaires related to caregiver activities, caregiver burden, and quality of life on a weekly basis throughout the six month span of the study.

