### Settings and Targeted Population

Ambulatory dementia patients will wear the localization device in these studies. However, the study participants actually providing data in these studies will be paid and unpaid caregivers. Study 2a will be conducted in the memory and skilled care units at Oak Hammock Senior Living Center in Gainesville, FL. Five ambulatory patients with moderate dementia (Mini-mental State Exam (MMSE) scores of 10-18) in each setting (memory/skilled) will be identified and with consent of their legal proxies included in

their study. Participants in Study 2a will include 10 persons with moderate dementia and their six paid caregivers at Oak Hammock Senior Living Center. These professional caregivers preside over multiple patients at one time, so only six paid caregivers are needed for these 10 patients. Separate day and evening shift assigned primary caregivers (typically certified nursing assistants) will be provided the smartphone tool used for monitoring location. Study 2b will be conducted with community dwelling dementia patients with mild dementia (MMSE 19-25). Participants in Study 2b will include 80 community dwelling persons with mild dementia and their 80 unpaid, family caregivers who all reside in the Gainesville, Florida area. Caregivers for these patients will have at least 3-times weekly contact with the patients. Cohabitation will not be required but will be recorded will caregiver relationship (spouse, adult child, other family, friend) as covariates. Presumed etiology of the dementia will be recorded but will not be a selection factor (Alzheimer's, vascular dementia, Lewy body dementia).

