#### *Measures and Devices Proposed*

Dementia patients will wear the provided insole inserted into their own shoes. The insole will have a small electronic sensor that measures acceleration, foot force, and/or orientation. The subject will then walk for a series of trials to determine the wearability while in motion. Data will be transmitted securely from the sensor system to the data collection device, a laptop or desktop computer. Once collected, the data file will be securely stored. Caregivers will complete paper records of caregiver activity, burden, and quality of life.

**Location Validation** Measures in Study A. For one-week prior to the formal efficacy trial, the technology will be deployed to all 10 participants. Once per shift at a randomly generated time, the paid caregivers a notification (a buzz on the smartphone) and asked to respond 1) location visually verified to be correct 2) location visually verified as incorrect or 3) unable to provide verification at that time due to other responsibilities. In the case of the last response, the system will auto generate another notification latter in that shift. Caregivers will be asked to verify location as either correct or incorrect at least one time per shift. Ten patients tracked at least twice per day over 7 days will provide 140 data points to assess the accuracy of the system at tracking patient location. An accuracy of less than 95% will result in our delaying the efficacy study until technical improvements can improve the accuracy of the deployed system.

**Primary Efficacy Outcome.** Primary outcome measure in both studies will be the Caregiver Activity Survey (Davis, et al., 1997). This well validated scale requires caregivers to report on amount of time spent caregiving for a particular patient. It has high test-retest reliability (.88) and documents an increase in time spent in supervision as MMSE declines overtime (Marin et al., 2000). Caregivers will be asked to complete this instrument once every two weeks.

**Secondary Efficacy Outcomes** in Study b. Caregivers in study b will also complete the short-form of the Zarit Caregiver Burden scale [32] and the AD Quality of Life Scale [33]. Both scales are reliable, well validated, and the most widely used measures of careburden and AD-QoL.

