### *Statistical Analysis Plan*

Practical considerations related to limited availability of the device determined the sample size. We can only recruit as many people as the number of devices we have to deploy over the course of the study.

Research assistants will review all data forms at time of collection and query participants immediately if data is missing. Research staff will double enter participant reported data in an electronic database (RedCap). Any data inconsistencies will be corrected by review of the source material. All data analysis will be conducted under the supervision of [name] using established statistical packages (e.g. SPSS).

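### Study 2a recruits five patients from each of two care units but states no stratification of sequence by care unit; randomising within unit would be a cheap gain in balance and precision.

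*Combined protocol and SAP*

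**What the plan says.** Section 6 of the protocol, under Settings and Targeted Population, sets a recruitment quota by care setting: "Five ambulatory patients with moderate dementia (Mini-mental State Exam (MMSE) scores of 10-18) in each setting (memory/skilled) will be identified". The total is ten patients, rated by six paid caregivers: "Participants in Study 2a will include 10 persons with moderate dementia and their six paid caregivers at Oak Hammock Senior Living Center".

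The Design subsection makes both studies crossovers ("Both studies will involve a counterbalanced within-subject design") of three months plus three months. The allocation rule is individual: "each target patient will randomly be assigned to either have the technology or not have the technology applied for a period of three months". For Study 2a the only added constraint is on the totals: "For Study 2a we will deploy 5 units during the initial 3 months and have 5 patients unmonitored". In that sentence the word units means insole devices. Below, care unit means memory care or skilled care.

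No section mentions stratifying, blocking or balancing sequence by care unit. The outcome concerned is caregiver-reported time: "Primary outcome measure in both studies will be the Caregiver Activity Survey". The secondary scales are assigned to Study 2b only. The Statistical Analysis Plan says "Practical considerations related to limited availability of the device determined the sample size" and names no model, and so no period, sequence or care-unit term. The only covariates mentioned, cohabitation and caregiver relationship, appear in the text on Study 2b.

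**The concern.** A crossover removes fixed differences between care units, because each patient is compared with himself or herself. It does not remove a change between the two epochs that happens in one care unit only, such as a change in staffing or routine, or a drift in how that unit's staff report time. These are possible causes; the documents report none of them.

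If most patients in one care unit receive the device first, such a change partly lines up with the switch of condition and moves the estimated device effect. Study 2a has some exposure to this. Its one efficacy outcome is a staff report, six staff members rate ten patients, and a change in one rater or one unit can move several patients together. Repeated ratings within an epoch do not average out a shift that lasts the whole epoch. With ten patients, an uneven split by chance is not rare.

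**Working it through.** The documents give no imbalance, power or precision figure for Study 2a, so there is nothing of theirs to reproduce.

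**Inputs.** Five patients per care unit and ten in total (Settings and Targeted Population); five monitored first and five unmonitored first (Design). Assumption: the five monitored-first patients are a simple random draw from the ten.

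**Chance of an uneven split.** Let k be the number from one given care unit who are monitored first. The number of allocations with that k is C(5,k) × C(5,5−k), out of C(10,5) = 252.

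| k | Split in that care unit | Allocations | Probability |
|---|---|---|---|
| 0 | 0:5 | 1 | 0.4% |
| 1 | 1:4 | 25 | 9.9% |
| 2 | 2:3 | 100 | 39.7% |
| 3 | 3:2 | 100 | 39.7% |
| 4 | 4:1 | 25 | 9.9% |
| 5 | 5:0 | 1 | 0.4% |

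With five monitored first overall, the other care unit always has the mirror-image split. A split of 4:1 or worse has probability (1 + 25 + 25 + 1)/252 = 52/252 = 20.6%. A 5:0 split has 2/252 = 0.8%. The remaining 200/252 = 79.4% are 3:2, the best attainable with five per care unit.

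**Leakage.** Take the usual period-adjusted crossover estimator: half the difference between the two sequence groups in mean period difference. Let d be a period shift present in one care unit only. The monitored-first group contains k of that unit's patients and the other group 5−k, so the contribution to the estimate is

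½ × [k/5 − (5−k)/5] × d = d(2k−5)/10.

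In size this is 0.1d at 3:2, 0.3d at 4:1 and 0.5d at 5:0.

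**Over the randomisation.** The mean is zero by symmetry. The mean square is (2×1×0.25 + 2×25×0.09 + 2×100×0.01)/252 = 7/252 = 0.0278, so the root mean square is 0.167d. If every allocation is 3:2, it is 0.10d.

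**Cost of a care-unit-by-period term.** Let s² be the variance of a patient's period difference.

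- Unadjusted, five against five: ¼(1/5 + 1/5)s² = 0.100s².
- Adjusted at 3:2, averaging two within-unit estimates: ½ × ¼(1/3 + 1/2)s² = 0.104s², about 4% more.
- Adjusted at 4:1: ½ × ¼(1/4 + 1)s² = 0.156s², about 56% more.
- At 5:0 the term is collinear with sequence, and the device effect cannot be estimated within care unit.

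The term takes residual degrees of freedom from 8 to 7 in a simple two-sequence analysis, so the 95% t multiplier goes from 2.306 to 2.365. At 3:2 the interval widens by √1.0417 × 2.365/2.306 = 1.021 × 1.026 = 1.047, about 5%, with residual variance unchanged.

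**The case against.** The strongest reply is that this is chance imbalance and not bias. Expected leakage is zero, and a one-unit shift also widens the spread of period differences, so on average it enters the standard error of an ordinary crossover analysis. Nearly four in five unstratified allocations already give the best possible split. No document shows that the two care units would change differently. All of that stands, and it limits the point to precision and to balance in the single allocation the study will get.

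A reader might infer that the plan deliberately allocates without regard to care unit. The documents do not support that: they neither describe nor exclude balancing by setting. The 20.6% therefore depends on the simple-draw assumption, and if stratification is intended, one sentence would settle the matter.

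It can also be said that mixed care units invite spillover, since the same staff then look after monitored and unmonitored patients together. This has little force against stratifying, because 79.4% of unstratified allocations produce the same 3:2 mix. The converse argument, that staff in a lopsided unit would see few patients in the opposite condition, assumes that staff stay in one care unit. The documents do not say so, and the leakage formula does not need it.

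Finally, the larger gap is that no Study 2a model exists. That is true, and it means the adjustment has to go into a model yet to be written. It does not change the case for a better randomisation list.

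**Conclusion.** The point holds as a modest design improvement. Care setting is used as a recruitment quota, but no use of it is stated in allocation or analysis. Under a simple draw of five from ten there is a 20.6% chance of a 4:1 or 5:0 split, and a one-unit period shift would then leak 0.3d or 0.5d, against 0.1d at best. The result rests on that draw, on a period-adjusted estimator that the documents do not specify, and on some non-zero d, for which they give no size.

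Two stronger readings should be resisted. The first is that the device effect is systematically biased; it is not, because the expected leakage is zero. The second is that an adjustment term alone would remove the problem free of charge; it costs about 56% in variance at 4:1 and fails at 5:0. The change is worth making because it is cheap and has to be made before patients are assigned.

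**What to change.** Randomise sequence within care unit: three of five monitored first in one and two of five in the other, with a random draw deciding which care unit gets three. This keeps five devices in use in each epoch and changes neither recruitment nor patient procedures. State the rule in the Design section; if stratification was already intended, say so there.

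When the Study 2a model is written, prespecify a care-unit-by-period term to remove the 0.10d that stratification leaves behind.

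The cost of stratifying is a different randomisation list. The cost of the term is one residual degree of freedom and the small widening of the interval shown above. If the care units do change differently, the term also takes that variation out of the residual, which would offset part or all of the widening.
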